## 9.2 PROPOSED ANALYSES

### 9.2.1 Primary Outcomes

- To compare using SVR rates the efficacy and compliance of DAAs in 135 new HCV positive individuals randomised to one of three groups; DOT, fortnightly therapy and fortnightly therapy with psychological adherence intervention.

The data for these outcomes will be generated directly from the CRFs from the clinical and laboratory data recorded therein.

### 9.2.2 Secondary Outcomes

- Compare adherence to therapy rates of subjects randomised to either DOT, fortnightly therapy or fortnightly therapy with psychological adherence intervention - treatment of HCV. Adherence rates will be obtained from the daily log data in the DOT group, and from pill counting and MEMs caps data in the two fortnightly therapy groups.
- Assess reinfection rates in the PWID population and treated using all oral DAA regimes. The data for reinfection rates will be generated from the annual follow up and retesting for chronic HCV infection of all participants treated. This will be from routine clinical follow data and consent will be sought to access this. The analysis is simple, requiring only simple descriptive statistics.
- Assess viral resistance patterns in participants who do not achieve SVR. These data will be obtained by analysing samples for resistance associated variants (RAVs) using standard clinical laboratory assays.
- Assess the types of illicit drugs taken by trial participants and identify any interaction with the DAAs and possible effect on adherence. This data will be generated by the adverse event reporting mechanism within the trial. The particular interest will be around interactions of the trial medication with drugs of misuse. Concomitant drug use during the trial will be recorded in the CRF at baseline and end of treatment and supported by urine toxicology from a urine sample that will be collected during treatment. Data will be recorded in the CRF.

### 9.2.3 Statistical analysis

Outcomes Data Analysis plan: Analysis of the trial will follow the principles outlined in the ICH E9 'Statistical Principles for Clinical Trials' and carried out by the UKCRC registered Tayside

Clinical Trials Unit (TCTU). Prior to data lock an agreed Statistical Analysis Plan (SAP) will be finalised covering the pre-specified statistical analysis.

The primary outcome of SVR will be assessed as a binary outcome for subjects and so will utilise logistic regression modelling. The numerator will be the number of subjects achieving SVR and the denominator will be total number of patients randomised to each arm. Additionally results will be expressed as a proportion of the estimated HCV infected subjects in needle exchange. The estimated number of infected patients will be based on national survey data and the empirical rate discovered in the trial (allowing for patients who refuse testing). A test of interaction between contingency and pathway will be carried out and if not significant contingency will be assessed independently. If significant then the effect of contingency will be assessed by each pathway separately. As all patients will have either achieved SVR or not and we will assume that drop-outs / lost to follow-up are failures, there will be no missing data in the primary outcome. Extra- binomial variability or over-dispersion will be examined in the logistic model and if present alternative modelling such as negative binomial models will be considered. This will also be adjusted by therapy and genotype; the two factors are interdependent determining length of therapy.

Secondary binary outcomes will be analysed in the same procedure, initially as intention to treat with all eligible patients as the denominator and then to explore the steps in the pathway by per protocol analysis in particular to analyse on treatment success:

- a) Proportion of HCV tested.
- b) Proportion who start HCV treatment within the duration of the study of those identified with HCV.
- c) Adherence: to compare the longitudinal evolution of adherence to the prescribed regimen between the conventional pathway and the pharmacy led pathway. For each patient, daily adherence will be defined using a binary variable  $Z_t$  indicating whether yes ( $=1$ ) or no ( $=0$ ) the subject has taken their medication on day  $t$ . This longitudinal binary variable will be directly generated from the patient electronically compiled dosing history. Comparison of binary time series is realized using a logistic regression where dependence among observations from a given patient over time is taken into account. The effect of pathway and contingency management on overall adherence will be tested using the above-described model by testing if either the group coefficient or the interaction between the group and time are significantly different from zero.
- d) Proportion who complete the course of those initiating treatment.

Multiple logistic regression modelling will explore the patient and pathway characteristics that are associated with the secondary outcomes and primary outcome. Patient outcomes considered will be age, gender, deprivation, employment, comorbidity, and the psycho-social variables assessed.

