We will recruit 135 participants and randomise them to one of three arms: daily, directly observed therapy; fortnightly dispensing of drugs; fortnightly dispensing of drugs with a psychological adherence intervention. Randomisation will be stratified according to HCV genotype. Participants will be treated for 12 weeks and followed up 12 weeks post treatment for the measurement of sustained viral response (SVR). The primary outcome measure will be SVR at 12 weeks post treatment (SVR12), as this measure of cure is the determinant of sufficient compliance and efficacy within the 3 treatment arms. Analysis will be by modified intention to treat of all participants who receive one dose of therapy, to show non-inferiority fortnightly dispensing is easier to deliver than daily dispensing.

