## 5.5 RANDOMISATION

### 5.5.1 Randomisation

After successful screening for eligibility and safety, participants will be randomised to either DOT, fortnightly pick up or fortnightly pick up with psychological intervention.

PWID who are eligible for this trial have unpredictable and chaotic lives. It is therefore possible that an individual will consent to take part, provide baseline information and have blood taken for safety and eligibility checking. If eligible they may be randomised. They may then not be seen at the needle exchange for a number of weeks or even months. It is standard clinical practice that pretreatment bloods are valid for a period of 6 months and therefore we will consider baseline bloods taken for the study to be valid for 6 months unless there is a clinical indication to repeat within that period. Any clinical decision on whether bloods need to be repeated within 6 months will be made by the CI. If a consented participant reappears after a period longer than 6 months has elapsed, a documented verbal check will be made to confirm that the individual continues to consent to taking part in the study. The bloods will be re-taken and eligibility will be based on the results of these new blood tests. The blood tests taken closest to the date of treatment initiation will be considered as the baseline data. The viral genotype will not be retested as NHS lab policy is to redo this test only after 5 years have elapsed. After 6 months the baseline CRF will also be repeated to provide up-to-date pretreatment information. In this case, the information originally collected in the baseline CRF will be filed but will not be entered into the electronic data management system (Openclinica) and will not form part of the analysed dataset. To ensure that the correct, most up-to-date baseline data is entered into Openclinica, baseline data will be entered once each participant has started their treatment.

As this is an un-blinded trial, the nurse, or delegated member of staff, and participant will be aware of which arm they are allocated to. Randomisation to each of the three trial groups will be stratified by genotype so that the proportion of genotype 1 vs genotype 3 infected participants will be the same in each group. The Tayside Clinical Trials Unit (TCTU) GCP-compliant online randomisation system, TRuST, will be used by the specialist nurse or delegated, trained member of staff to perform the randomisation.

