## **9 STATISTICS AND DATA ANALYSIS**

### **9.1 SAMPLE SIZE CALCULATION**

Statistical analysis will be conducted in compliance with TASC SOPS.

We propose to conduct this project as a randomised trial to show that DAA therapy in very active PWIDs administered fortnightly with or without adherence intervention is non-inferior to DOT. We will compare pathways sequentially comparing DOT vs fortnightly delivery and then DOT versus fortnightly pickup with adherence intervention. Fortnightly pick up will be more cost effective than the other two options so long as adherence and efficacy matches that of the DOT and fortnightly plus adherence intervention. If we assume a 95% SVR rate (based on published studies) in the DOT arm of the trial in this population and a non-inferiority limit of 14% (which would be likely to maintain cost-effectiveness) then at a 5% significance level and 90% power

we would need a sample size of 42 in each group 126 in total. To allow for drop-outs we will aim to recruit 135 individuals, 45 per group.

A Statistical Analysis Plan (SAP) will be prepared for analysis of primary and secondary outcomes and will include a plan for handling missing data

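### Section 9.2.3 plans an over-dispersion check and negative binomial fallback that do not suit one yes/no SVR value per person, and it does not link its logistic model to the 14-point limit behind the sample size

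*Protocol*

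**What the plan says.** **Design (protocol, 9.1).** The aim is to show that DAA therapy "administered fortnightly with or without adherence intervention is non-inferior to DOT". The inputs are "If we assume a 95% SVR rate (based on published studies) in the DOT arm" and "a non-inferiority limit of 14% (which would be likely to maintain cost-effectiveness", with 5% significance and 90% power. The result is 42 per group, raised to 45 (135 in total) for drop-outs. DOT is compared first with fortnightly pick-up and then with fortnightly pick-up plus the adherence intervention.

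**Analysis (protocol, 9.2.3).** "The primary outcome of SVR will be assessed as a binary outcome for subjects and so will utilise logistic regression modelling". The denominator is everyone randomised to the arm. Every participant has a result, because "we will assume that drop-outs / lost to follow-up are failures". The same paragraph then states that "over-dispersion will be examined in the logistic model and if present alternative modelling such as negative binomial models will be considered", and that the model is also adjusted for therapy and genotype. Section 5.5.1 adds: "Randomisation to each of the three trial groups will be stratified by genotype".

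Section 9.2.3 does not mention non-inferiority, the 14% limit, an interval or a risk difference. A SAP is promised before data lock.

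**The concern.** There are two separate matters.

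**The over-dispersion sentence (main point).** Over-dispersion is a property of grouped binomial counts or of event counts. By the section's own description, the primary outcome is one yes/no value per person with none missing. A diagnostic that carries no information is tied to a fallback from the wrong family. If the fallback were used with model-based errors, the intervals would be far too wide to show non-inferiority.

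**The missing link to the limit (secondary point).** The trial is sized on an absolute difference in SVR, but the only model named for the primary outcome has the odds ratio as its natural scale. Nothing says how its output is to be set against 14 points. An analyst who carried the limit over to the odds-ratio scale could reach the opposite verdict on the same data.

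**Working it through.** **1. Reproducing the sample size.** Inputs from 9.1: 95% SVR in DOT, limit 14%, 5% significance, 90% power. Equal SVR in the fortnightly arm is assumed, as its rate is not stated.

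n = 2(0.95)(0.05)(1.645 + 1.282)² / 0.14² = 41.5, so 42 per group, 3 × 42 = 126.

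Alternatives that do not give 42:
- one-sided 2.5%: 51
- a relative 14% limit (0.14 × 95 = 13.3 points): 46
- a log odds-ratio limit (step 5): 162

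The limit that sized the trial is therefore 14 percentage points at one-sided 5%.

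**2. Dispersion with arm terms only.** The fitted probability in arm k is its observed proportion p_k. Within the arm, the sum of (y − p_k)² / [p_k(1 − p_k)] equals n_k exactly. Over three arms the Pearson statistic is 135 on 135 − 3 = 132 degrees of freedom, so the ratio is 1.0227 whatever the SVR counts, provided each arm has at least one success and one failure. Simulation gave 1.0227 every time, with constant and with strongly varying individual SVR probabilities.

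**3. Dispersion with genotype added, as planned.** The ratio is no longer constant, but it varies by chance only. The simulations had independent 0/1 outcomes, no over-dispersion and an assumed 15:30 genotype split per arm, because the protocol gives no split.
- SVR 95%: about 0.83 to 1.76 (these extremes depend on the run).
- SVR 93% and 86% by genotype: central 95% of values 0.92 to 1.19.

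Grouping the data into 3 × 2 arm-by-genotype cells leaves 6 − 4 = 2 residual degrees of freedom. Those measure arm-by-genotype interaction, not extra-binomial variation.

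**4. The negative binomial fallback.** Its variance is at least its mean, 0.95. The true variance is 0.95 × 0.05 = 0.0475, and 0.95 / 0.0475 = 20. In 40 trial fits the dispersion parameter went to its zero boundary (about 0.00002), which leaves a Poisson model. With model-based errors, two arms of 45 with equal 95% SVR would have a 90% lower limit for the rate ratio of exp(−1.645 × √(2 / (0.95 × 45))) = 0.70. The ratio corresponding to the 14-point limit is 81/95 = 0.853 (my conversion; the protocol states no ratio margin). Even identical arms would fail.

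**5. What the missing link could cost (illustration only).** At 95% against 81%, OR = (0.81/0.19) / (0.95/0.05) = 0.224. At a DOT rate of 90% a 14-point loss is OR 0.352, and holding 0.224 there would tolerate a 23.1-point loss.

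Power by exact enumeration, 45 per arm, both arms at 95%, one-sided 5%:

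| Rule | Power |
|---|---|
| Risk difference, Wald | 89.9% |
| Risk difference, score-type | 84.7% |
| OR against 0.224 | 38% to 47%, by test |

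For 90% power the OR rule needs 2(2.926)² / (0.0475 × (ln 0.2244)²) = 161.5, so 162 per arm.

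Same data, opposite verdicts:
- DOT 43/45, fortnightly 42/45: score lower limit −11.8 points (passes); OR 0.65, Wald lower limit 0.139 (fails).
- DOT 40/45, fortnightly 38/45: score lower limit −16.9 points (fails); OR 0.68, Wald lower limit 0.242 (passes).

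An arm of 45 has no failures with probability 0.95^45 = 0.099, and at least one of three arms with 1 − (1 − 0.099)³ = 0.27. The maximum-likelihood arm coefficient is then not finite.

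**The case against.** **On the model.** Effect measure, interval and decision rule are commonly left to a SAP, and one is promised. Logistic regression can deliver a standardised risk difference, and 9.2.1 and 9.2.3 speak of SVR rates with a numerator and denominator, which suits a comparison of proportions. All of this stands. A reader might infer that the protocol will judge non-inferiority on the odds ratio, or that 9.2.3 contradicts 9.1. The text does not support either: it states no odds-ratio margin and no odds-ratio null. The figures in step 5 show one unfavourable reading, not the plan.

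**On over-dispersion.** A reader might also say that the dispersion ratio is fixed at 1.02 in the planned analysis. That is true only for arm alone; with the genotype adjustment it varies. This does not rescue the check, because the variation is noise. Treatment is delivered through several needle exchanges and pharmacies, so outcomes could be correlated within sites. But 9.2.3 describes no such grouping, and a negative binomial would still be the wrong family for a bounded outcome. The wording is tentative (a fallback to be considered), which lowers the chance of harm but does not make the rule valid.

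**Conclusion.** The main point holds with high confidence and does not depend on the SAP: for SVR the over-dispersion check is uninformative, and the fallback overstates the variance at least 20-fold at 95% SVR. It rests on one 0/1 value per participant, which 9.2.3 itself states. The simulated range also rests on the assumed genotype split; the protocol sets no trigger value, so how often the fallback would be invoked cannot be given.

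The secondary point is a missing link that is cheap to supply. It does not fault the sample size, which reproduces at 42, nor the choice of logistic regression. The drop from about 85–90% power to 38–47% applies only if the limit were carried over as OR 0.224, with equal 95% SVR and one-sided 5%.

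**What to change.** 1. Delete the sentence on over-dispersion and negative binomial models for SVR.
2. Add one sentence to 9.2.3: each fortnightly arm is compared with DOT, in the order given in 9.1, on the genotype-adjusted SVR12 risk difference (stratified, or standardised from the logistic model); non-inferiority is declared if the lower limit of the two-sided 90% interval is above −14 points; the odds ratio is supportive. The 90% level matches the one-sided 5% that reproduces 42.

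The interval method can stay in the SAP, but it should remain valid when an arm has no failures.

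The wording costs two edits. The choice of interval has a price that should be stated. At 95% SVR in both arms a score-type interval has 84.7% power at 45 per arm (91.0% would need 54), with 4.7% error at the limit. A Wald interval keeps 89.9% at 45 but has 6.3% error at the limit. The power or error quoted in 9.1 should match the method chosen.

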## 1.2 RATIONALE FOR TRIAL

Oral anti-HCV regimens that are interferon free and have virtually no side-effects are now the standard of care in conventional treatment populations. The medication should be taken daily to optimise therapeutic success, and if adherence is poor in the actively injecting population it is possible that the effectiveness of the new oral drugs will be reduced. It is key to know if all oral directly acting antivirals (DAA) regimens are robust and maintain SVR rates in this population. The real world SVR rate combined with drug cost, re-infection rate and emergence of viral resistance will determine if this treatment as prevention model is cost-effective with DAAAs. Directly observed therapy (DOT) is the ultimate adherence aid, but it is more costly and draconian so that it may discourage participants, especially this group, from taking up therapy. Therefore we need to demonstrate that treatment uptake and adherence is sufficient to maintain the SVR rate at a level which makes treatment as prevention cost effective. We will compare three means of delivery: daily DOT vs fortnightly pick up of therapy vs. fortnightly pick-up of therapy with a psychological intervention for adherence. The DOT method of treatment has not been explored in this difficult to find and engage population previously. Contingency management in the form of protein drinks for successful completion of each fortnight of treatment will be provided in all three arms of the trial. A comparison of the three pathways mentioned above will show which pathway shows best acceptability to participants and greatest compliance

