### 3 TRIAL DESIGN

#### 3.1 TRIAL DESCRIPTION

This is a randomised, un-blinded trial which will be conducted in the needle exchange services and pharmacies across Tayside, designed to evaluate the efficacy and feasibility of DAA therapy, in HCV positive, genotype 1 and 3, active PWIDs, administered via three different routes:

1. DOT,
2. Fortnightly pick-up
3. Fortnightly pick-up with psychological intervention.

Participants included in the trial will have a reactive Dry Blood Spot (DBS) test to confirm HCV infection, PCR to confirm active infection and will currently be using illicit drugs, as confirmed by the participant. Drug screening (by urine sample) will not be tested at that time.

Participants will be stratified by the genotype of their HCV infection; genotype 1 vs genotype 3 and randomised to one of three groups; DOT, fortnightly pick-up, or fortnightly pick-up with psychological adherence intervention.

All PWID are encouraged to have a DBS test annually as part of clinical practice in Tayside. Upon receipt of a reactive DBS test, potential participants will be briefed about the trial by the specialist nurse or other trained member of staff and given a participant information sheet (PIS) informing them of what is involved. Willing individuals will provide written informed consent and will then have safety bloods drawn to determine eligibility to proceed. A full list of inclusion/exclusion criteria is detailed in section 4.

Participants in all three arms of the trial will attend a baseline visit, a randomisation visit either one (genotype 3) or two (genotype 1) visits during treatment, an end of treatment visit and an SVR visit, as detailed in Appendix 2.

All participants will be given incentives to continue with their treatment in the trial. These will consist of protein drinks and will be given at each study visit.

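### Section 9.2.3 tests a contingency effect that every arm receives, compares two pathways that are not trial arms, and takes daily adherence from electronic data that no DOT participant has

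*Protocol*

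**What the plan says.** **Contingency.** For the primary outcome, section 9.2.3 states: "A test of interaction between contingency and pathway will be carried out and if not significant contingency will be assessed independently". If the interaction is significant, the contingency effect is to be assessed within each pathway. For adherence, item c) states: "The effect of pathway and contingency management on overall adherence will be tested using the above-described model". Section 1.2 says of the incentive: "Contingency management in the form of protein drinks for successful completion of each fortnight of treatment will be provided in all three arms". Section 3.1 says: "All participants will be given incentives to continue with their treatment in the trial".

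**Groups compared.** Item c) plans "to compare the longitudinal evolution of adherence to the prescribed regimen between the conventional pathway and the pharmacy led pathway". Section 9.2.2 plans something else: "Compare adherence to therapy rates of subjects randomised to either DOT, fortnightly therapy or fortnightly therapy with psychological adherence intervention".

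**Data source.** Item c) defines, for each patient, a yes/no variable for every day of treatment, and adds: "This longitudinal binary variable will be directly generated from the patient electronically compiled dosing history". Section 9.2.2 differs by arm: "Adherence rates will be obtained from the daily log data in the DOT group, and from pill counting and MEMs caps data", the last two being for the fortnightly groups. Sections 3.1 and 6.1.4 place the electronic caps on Sovaldi bottles, which only genotype 3 participants receive. DOT participants are handed one tablet of each drug per day, and this is recorded in a log. Zepatier in the fortnightly arms comes in blister cards, and leftover tablets are counted every two weeks.

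**The concern.** The complaint is not that detail is missing. Section 9.2.3 states analyses that the design in sections 1.2, 3.1, 5.5.2 and 6.1.4 rules out.

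A factor that every participant receives has no comparison group, so neither its effect nor its interaction with arm can be estimated. A two-pathway contrast with undefined labels does not say how three arms are to be compared. A data source that contains no DOT participant cannot deliver a comparison with DOT.

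Adherence is a stated secondary outcome (section 2, Table 2, and section 6.4). Section 9.1 also makes the cost-effectiveness argument for fortnightly pick-up conditional on adherence, as well as efficacy, matching the other arms. As written, sections 9.2.2 and 9.2.3 give different groups and different sources for the same outcome. The analyst of an open-label trial would have to choose replacements that the protocol does not specify.

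**Working it through.** **The plan's own figure.** The only computed figure in the protocol is the sample size in section 9.1: 95% SVR, margin 14 percentage points, 5% significance, 90% power. With one-sided 5%:

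n = (1.645 + 1.282)² × 2 × 0.95 × 0.05 / 0.14² ≈ 8.56 × 0.095 / 0.0196 ≈ 41.5, so 42 per group and 126 in total.

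This reproduces the stated figure. The present point does not depend on it, but the planned 45 per arm (135 in total) are the denominators below.

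**1. Contingency.** Code the model that the SVR test implies: intercept, arm 2, arm 3, contingency, contingency × arm 2, contingency × arm 3. Sections 1.2 and 3.1 set contingency to 1 for all 135 participants. Then:

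- contingency = intercept
- contingency × arm 2 = arm 2
- contingency × arm 3 = arm 3

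The matrix has 6 columns and rank 3. The three independent columns are the intercept and the two arm terms, so no contingency term is estimable. In the longitudinal adherence model, contingency × time equals time and is not estimable either. The group and group-by-time tests that item c) names can be estimated once the groups are defined, but they say nothing about contingency.

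**2. Groups.** Side by side:

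| Section | Groups |
|---|---|
| 3.1, 5.5.1 | DOT; fortnightly; fortnightly plus psychological intervention |
| 9.1 | DOT v fortnightly; DOT v fortnightly plus intervention |
| 9.2.2 | the three arms |
| 9.2.3 c) | conventional pathway; pharmacy-led pathway |

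The last two labels appear nowhere else and are mapped to no arm.

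**3. Daily electronic data.** Source by arm and genotype:

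| | Genotype 1 | Genotype 3 |
|---|---|---|
| DOT | daily log | daily log |
| Fortnightly arms | fortnightly tablet count | fortnightly tablet count (Zepatier) and electronic cap (Sovaldi) |

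Let p be the share with genotype 3. The protocol does not give it, so p is an assumption. Randomisation is stratified by genotype, so about 45p participants per arm are genotype 3. Those with an electronic history number 2 × 45 × p = 90p:

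| p | With history | Share of 135 | Without |
|---|---|---|---|
| 0.3 | 27 | 20% | 108 |
| 0.5 | 45 | 33% | 90 |
| 0.7 | 63 | 47% | 72 |
| 1 (ceiling) | 90 | 67% | 45 |

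The 45 without a history at the ceiling are the whole DOT arm.

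A genotype 1 participant in a fortnightly arm yields 12 / 2 = 6 tablet counts, against the 12 × 7 = 84 daily values that the model needs. A count gives how many of 14 tablets were missed, not on which days. Two missed tablets, for example, fit 14 × 13 / 2 = 91 different daily patterns.

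**The case against.** **Pharmacy-led may mean DOT.** The protocol uses pathway for its arms, and community pharmacists dispense and observe DOT. This is a possible guess, and the problem would then be partly one of labels. But section 5.5.2 also allows DOT at the needle exchange, no section makes the link, and two groups still do not match the three-arm comparison in 9.2.2.

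**Receipt of the drinks may vary.** Section 1.2 ties them to completing a fortnight, section 3.1 to study visits. An analysis by drinks received could be fitted, so the rank result holds for contingency as assigned. But receipt would be a consequence of adherence or attendance after randomisation, and its association with SVR or adherence would not be a contingency effect.

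**Daily or other adherence data exist elsewhere.** The DOT log can give a yes/no for observed days, and section 6.4 has fortnightly participants asked about adherence at visits. Both are true. The log is not the electronic source that item c) names, however, and doses handed out for weekends and closed days (section 5.5.2) are not observed. Questions at visits give no daily series. Table 2 in section 2 does not limit the caps by arm, but sections 5.5.2, 6.1.4, 6.4 and 9.2.2 together place them in the fortnightly arms.

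**The SAP can settle this.** It can choose the adherence measure and model, and parts of the remedy below are a choice among reasonable options. That does not remove contradictions from the protocol text. It is also fair that section 9.1 mentions adherence in a single cost-effectiveness sentence and bases the sample size on SVR alone.

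**Conclusion.** The point holds in all three parts. The contingency main effect and interaction cannot be estimated for SVR or adherence while contingency is given to everyone (rank 3 of 6). Item c) compares two groups that correspond to no stated arm. Its data source covers at most 90 of 135 participants and none of the 45 in DOT, so it cannot give the comparison with DOT that section 9.2.2 plans.

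The rank result and the 90-of-135 ceiling follow from the protocol and the planned 45 per arm. The 20% to 47% coverage rests on an assumed genotype 3 share of 30% to 70%.

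The SVR comparison by arm and the sample size are not affected. The text should be corrected, but the point does not threaten the primary result.

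**What to change.** In section 9.2.3:

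- Delete the contingency main-effect and interaction tests for SVR and for adherence.
- In item c), name the three randomised arms and use the sources in section 9.2.2.
- As the measure available in every arm, use the percentage of prescribed Zepatier doses taken (daily log in DOT, returned-tablet count in the fortnightly arms), adjusted for genotype.
- Name fortnightly v fortnightly plus intervention as the contrast that is measured the same way in both arms.
- Keep the DOT v fortnightly adherence comparison. State that the measurement source differs by arm and that DOT doses handed out for closed days are not observed.
- Confine the daily binary model to genotype 3 participants in the two fortnightly arms, where the electronic caps are used.

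The cost is protocol wording, with matching wording in the SAP. Sample size, visits and data collection stay as they are, because logs, returned packs and cap records are already planned. The small downside is that the daily model is then openly limited to fewer participants and two arms.
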